## **9.2. Sample size calculations**

### *Primary objective*

For the primary objective, sample size calculations are complicated due to the variability of cough frequency between different patients with different conditions. To evaluate the system's capacity to detect and classify coughs based on their etiology, we will create and prospectively

increase a split-sample (derivation / validation) dataset and test performance until it plateaus (see data analysis). Based on previous digital cough diagnostic studies performed by the co-investigators, we anticipate needing 15,500 individual cough data points and 200 cough time series by groups for every individual diagnosis. This number of coughs might be rapidly reached by participants diagnosed with a cause of chronic cough but will likely take substantial time for other acute conditions. Thus, the suggested duration of 5 years.

To evaluate the capacity of the system to reflect changes in cough frequency associated to clinical evolution, sample size calculations are more straightforward and detailed below.

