### **7.2. Efficacy variables**

For the primary objective 1, efficacy will be measured by determining Hyfe's capacity to predict a diagnosis, or reflect clinical evolution of patients, based on cough signatures. For this, the acoustic characteristics of coughs (mean frequency, volume, amplitude) registered from participants with an etiologic diagnosis, will be described, to identify patterns associated to specific conditions. Additionally, the Area Under the Curve, sensitivity, and specificity of the AI system will be retrospectively evaluated with the annotated cough registries.

For the secondary objective 1, the efficacy variable will be the daily score in the online VAS, and the coughs per recorded hour.

For the secondary objective 2, there is no clear efficacy variable. We will retrospectively include anonymous coughs registered in patients with an etiologic diagnosis and annotated with data in online datasets from where they can be used to train this and similar AI systems in the future.

For the secondary objectives 3 and 4, efficacy variables will include the calculated sensitivity, specificity, positive predictive value (PPV), and negative predictive value (NPV) of Hyfe, compared to two trained human observers.

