## 9. STATISTICS

### ***9.1. Description of the statistical methods to be used, including the schedule of all the planned intermediate analyses***

For completion of the primary objective

To assess the accuracy of the cough surveillance system to detect cough patterns associated to specific diseases, we will use participants in which an etiologic diagnose is reached before completion of the study. We will search for digital footprints of singular detected cough events, and/or the pattern of cough in time for participants with a given diagnosis.

These records will be used to train a previously developed convolutional neural network to perform respiratory disease cough classification. We will initially use a random split-sample approach (70% derivation & 30% validation) to assess the performance of the newly generated cough classification tool (sensitivity, specificity, positive and negative predictive values, AUC). Performance will then be validated by retrospectively analyzing these participants' coughs with the newly trained AI-network.

The cough classification tool will be supplemented with patient-specific information to assess the incremental value of cough-based multi-variable prediction.

For secondary objective 1

The daily VAS score of participants will be compared to the cough frequency registered by the cough surveillance system. These data will be used to fit a linear regression model to compare self-reported VAS scores to daily cough frequency and calculate a correlation coefficient ( $r$ ). The

average weekly VAS score and cough frequency on week 1, will be compared to that at study withdrawal using a paired t-test, and represented using before-after plots. P values below 0.05 will be considered significant. A similar approach will be used to compare results of the LCQ at the beginning vs the end of the study. Before-after plots will be constructed to represent these differences. This approach is also expected to provide information on the system's capacity to reflect clinical evolution of participants (Primary objective).

For completion of secondary objective 2

Cough registries of participants with an etiologic diagnosis of respiratory disease will be included in annotated datasets. There are no specific statistical analysis required for completion of this objective.

For completion of secondary objectives 3 and 4

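### Diagnostic classification (primary objective): the split sample that decides when to stop collecting data also supplies the reported accuracy, the plateau is undefined, and no untouched test set is kept

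*Combined protocol and SAP*

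**What the plan says.** Section 9.2 of the combined protocol and SAP explains why the classification part of the primary objective has no formal calculation: "sample size calculations are complicated due to the variability of cough frequency between different patients with different conditions". The rule offered instead is to "increase a split-sample (derivation / validation) dataset and test performance until it plateaus", with a pointer to the data-analysis section. A planning figure follows: "we anticipate needing 15,500 individual cough data points and 200 cough time series by groups for every individual diagnosis". Its basis is given as "Based on previous digital cough diagnostic studies performed by the co-investigators". The study may run for up to five years (sections 1.6 and 9.2).

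Section 9.1 says what the split is for: "We will initially use a random split-sample approach (70% derivation & 30% validation) to assess the performance". The measures it lists for the new classifier are sensitivity, specificity, both predictive values and the AUC. A further step comes after that: "Performance will then be validated by retrospectively analyzing these participants' coughs with the newly trained AI-network". Section 7.2 names the matching efficacy variables: "the Area Under the Curve, sensitivity, and specificity of the AI system will be retrospectively evaluated with the annotated cough registries".

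The documents do not state the plateau metric, its tolerance, the number or timing of looks, a minimum or maximum size, the unit of the split (cough or participant), or which look or network version will be reported. No third portion of data is reserved. The heading of 9.1 announces a schedule of intermediate analyses, but none is given for these looks.

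**The concern.** If validation results are consulted each time the dataset grows, and collection ends when they stop improving, the validation part takes part in a design decision. It is then no longer a clean test set, even if the split is strictly by participant. Two things are at stake.

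- **Early stopping.** With few validation participants per diagnosis, a flat stretch can arise by chance while the network is still improving.
- **Optimism.** If the validation results also influence which network, cut-off or look is reported, the headline accuracy is too high. By then every diagnosed participant may have been used, so no fresh data would remain in the study to correct it.

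Accuracy is a main efficacy variable of the only primary objective, so it should be clear in advance which data it comes from.

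**Working it through.** **1. The plan's own figure.** The 15,500 coughs and 200 series per diagnosis cannot be reproduced. The classification part states no target accuracy, precision, significance level or power. What can be derived is the validation share: 0.30 × 200 = 60 series and 0.30 × 15,500 = 4,650 coughs per diagnosis.

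**2. Precision of one look.** Assume one series per participant, a true AUC of A = 0.80, and 60 participants with the diagnosis against 60 without. The Hanley-McNeil formula is

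SE² = [A(1-A) + (m-1)(Q₁-A²) + (n-1)(Q₂-A²)] / (mn), with Q₁ = A/(2-A) and Q₂ = 2A²/(1+A).

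- Q₁ = 0.8/1.2 = 0.6667; Q₂ = 1.28/1.8 = 0.7111.
- SE² = [0.16 + 59(0.0267) + 59(0.0711)]/3600 = 0.001647, so SE = 0.041.
- The 95% half-width is 1.96 × 0.041 ≈ 0.08.

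For sensitivity on 60 participants, 1.96√(p(1-p)/60) gives ±0.116, ±0.101 and ±0.076 at p = 0.70, 0.80 and 0.90.

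**3. Noise between looks.** A plateau is judged on differences between overlapping looks, so the single-look SE is not enough. Take looks at 54 and then 60 per group with no true change.

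- Same network at both looks: for nested samples the variance of the difference is SE²(54) - SE²(60) = 0.001832 - 0.001647 = 0.000185, an SD of about 0.014.
- Network retrained between looks, with an assumed correlation of 0.7 between a participant's two scores: the simulated SD is about 0.035.

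Both exceed a tolerance such as 0.01 (assumed, since the plan gives none).

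**4. Consequences, by simulation.** No setting below comes from the documents.

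| Setting | Result |
|---|---|
| True AUC rising from 0.68 at 40 per group to 0.82 at 200; look every 20; stop after 2-3 looks without a gain above 0.01 | Stops before 200 per group in 64-89% of runs, at a mean true AUC of 0.77-0.80 |
| Same, last look reported | Bias about -0.01 |
| Same, best look reported | Bias about +0.03 |
| Same, best of five network versions reported | Bias about +0.06 to +0.07 |
| True sensitivity constant at 0.80; 6 or 12 new validation participants per look; stop when the change or gain is below 0.01 or 0.02; last look reported | Bias about -0.03 to +0.01; mean stopping size about 15 to 107 |
| Same, best look reported | Bias about +0.04 to +0.10 |

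When sensitivity was allowed to rise in the second model, the last look ran from about -0.05 to 0.00 and the best look from about +0.08 to +0.12. The largest values come from looks with very few validation participants. Interval coverage is not used as evidence here: at these sizes the simple interval under-covers even with a fixed sample (0.87 at 24 participants).

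**5. Is there independent data elsewhere?** The follow-on validation in 9.1 runs the new network on the same participants, possibly including those it was trained on. Section 7.2 uses the same annotated registries. Neither supplies untouched data.

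**The case against.** The strongest reply is that stopping on a plateau does little harm to the estimate by itself. With the last look reported, the bias is near zero or slightly negative. The overstatement needs an extra step, reporting the best look or version, and the plan nowhere says that will be done. New participants also join at each look, so this is not repeated use of one fixed set. This stands. A reader might infer that the stopping rule necessarily inflates the reported accuracy; the documents do not support that. They neither announce nor exclude selective reporting.

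A reader might also infer that the whole primary objective lacks a sample size. It does not: section 9.2 sizes the clinical-evolution part through secondary objective 1. Nor is the plan wholly open-ended, since it anticipates 15,500 coughs and 200 series and has a five-year limit. These are an expectation and an outer bound, however, and neither overrides the plateau rule.

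Section 9.2 does not say that the plateau is read on the 30% part. That remains an inference, supported by its pointer to the analysis section and by the absence of any other test data.

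Finally, moving the plateau judgement into cross-validation would not by itself cure early stopping. In a similar simulation, judging on the whole 70% share, as an optimistic stand-in, still stopped before 200 per group in 53-87% of runs, against 66-91% on the 30% share. The rule itself must therefore be specified.

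**Conclusion.** The point holds for diagnostic classification only. The plan has an undefined stopping rule, most naturally read as applied to the validation data, and it names no accuracy data untouched by stopping or model choice. About 60 validation series per diagnosis (one per participant assumed) give an AUC standard error near 0.04, so a flat spell is weak evidence of a plateau and stopping may come early.

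Overstatement of accuracy is conditional. It is about +0.03 to +0.10 in most of the assumed settings, and only if the best look or version is reported or the validation data guide model choices. With the last look alone it is about -0.03 to +0.01. How often collection would stop early, and the size of any bias, depend on a rule the plan does not give.

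This should be fixed. It does not invalidate the study: this part sets no hypothesis test or accuracy threshold. It is easy to correct before the data are scored and hard to correct afterwards.

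**What to change.** Amend sections 9.1 and 9.2 as follows.

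1. Pre-specify the plateau rule: metric, tolerance, look schedule, and minimum and maximum size per diagnosis. Judge it by participant-grouped cross-validation within the derivation data only.
2. Make the 30% part the final test set. Allocate it at random by participant at enrolment, and do not score it until the network and cut-off are frozen. Training then keeps its planned 70%.
3. Score the test set once and report that result, with confidence intervals, as the primary accuracy. Label the re-analysis of the same participants' coughs as apparent performance, not validation.

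The cost is protocol and SAP wording plus a locked allocation list. The downsides are that interim monitoring must rely on cross-validation within the 70%, and that the final accuracy keeps the limited precision of about 60 series per diagnosis (roughly ±0.10 for a sensitivity of 0.80).

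### The diagnostic target sets no number of patients per disease, and the plan does not fix whether sensitivity and AUC are counted over coughs or over patients

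*Combined protocol and SAP*

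**What the plan says.** Section 3 of the protocol gives the primary objective as the value of AI cough monitoring for screening, diagnosing and managing respiratory disease in practice. Those are uses for a patient.

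Section 9.2 (Primary objective) describes the task as sorting coughs by cause. It notes that "sample size calculations are complicated due to the variability of cough frequency between different patients with different conditions", and then states: "we anticipate needing 15,500 individual cough data points and 200 cough time series by groups for every individual diagnosis". On how fast the target fills, it adds: "This number of coughs might be rapidly reached by participants diagnosed with a cause of chronic cough". The dataset is to be enlarged, and performance tested, until performance levels off.

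On the signal, section 9.1 says: "We will search for digital footprints of singular detected cough events, and/or the pattern of cough in time for participants with a given diagnosis". On assessment, it says: "We will initially use a random split-sample approach (70% derivation & 30% validation) to assess the performance of the newly generated cough classification tool". The measures listed are sensitivity, specificity, predictive values and AUC. Section 7.2 says that "the Area Under the Curve, sensitivity, and specificity of the AI system will be retrospectively evaluated with the annotated cough registries".

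None of these sections gives a number of patients per diagnosis, a cap per patient, the unit over which accuracy is counted, a rule that turns many coughs into one diagnosis, or any allowance for coughs being clustered within patients.

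**The concern.** A diagnostic sensitivity should say how often a patient with the disease is identified. If it is computed over coughs, each patient counts in proportion to how often they cough. The result then describes mainly the most frequent coughers with each disease. It can lie well above or well below the proportion of patients correctly identified.

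Coughs from one person also resemble each other, so 4,650 coughs carry much less information than 4,650 independent observations.

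This is separate from how the 70/30 split is made. Splitting by patient prevents the same person from appearing in both parts, but it does not change what a per-cough sensitivity measures or how precise it is. Because the unit is not stated, it could also be chosen after results are seen.

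**Working it through.** **The plan's figure.** The 15,500 coughs and 200 series cannot be reproduced. Section 9.2 rests them on the co-investigators' earlier studies and gives no expected accuracy, precision, power or within-patient correlation. The checks below ask what the figures imply.

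**1. How few people could supply 15,500 coughs?** Section 4.1 (Monitoring period) gives outpatients an initial month, taken here as 30 days.
- One participant: 15,500 / (30 × 24) = 21.5 coughs per hour (32.3 per hour if monitored 16 hours a day).
- Five participants: 15,500 / (5 × 30 × 24) = 4.3 per hour.
- At an assumed 2 per hour: 15,500 / (2 × 24 × 30) = 10.8, so about 11 participants.

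The documents give no cough rate, so these rates are assumptions. The only per-person volume is in section 6: about 700,000 / 62 = 11,290 sounds per participant. These are putative coughs, not confirmed ones.

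**2. What does the second target add?**
- One series per participant: 200 patients per diagnosis, averaging 15,500 / 200 = 77.5 coughs each.
- Daily series over one month: 200 / 30 = 6.7, so about 7 outpatients. A 30% validation part would then hold about 0.3 × 6.7 = 2 people.

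**3. Per-cough against per-patient accuracy (assumed values).**
- Five patients. One supplies 80% of the coughs, with 95% of them classified correctly. Four share the rest at 50%.
  - Per cough: 0.8 × 0.95 + 0.2 × 0.50 = 86%.
  - Averaged over patients: (0.95 + 4 × 0.50) / 5 = 59%.
- Ten patients. One supplies 12,000 coughs at 95% and nine share 3,500 at 40%.
  - Per cough: (11,400 + 1,400) / 15,500 = 82.6%, yet a majority rule identifies 1 patient of 10.
  - With the two rates exchanged: (4,800 + 3,325) / 15,500 = 52.4%, and 9 of 10 are identified.

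The error can therefore go in either direction.

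**4. Precision, on the favourable reading of 200 patients.** The 30% validation part holds 0.3 × 15,500 = 4,650 coughs from 0.3 × 200 = 60 patients. Sensitivity is assumed to be 80%, and the half-width is 1.96 × √(p(1 − p)/n).
- Coughs treated as independent: 1.96 × √(0.16 / 4,650) = ±1.15 points.
- One result per patient: 1.96 × √(0.16 / 60) = ±10.1 points.
- For assumed sensitivities of 70% and 90%: ±1.32 against ±11.6 points, and ±0.86 against ±7.6 points.

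These two intervals are for different quantities. For the per-cough quantity itself, the correction is the design effect 1 + (m − 1) × ICC, with m = 77.5 coughs per patient if counts are equal:

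| Assumed ICC | Design effect | Effective n | Half-width (points) |
|---|---|---|---|
| 0.05 | 4.8 | 964 | ±2.5 |
| 0.1 | 8.7 | 538 | ±3.4 |
| 0.3 | 23.9 | 194 | ±5.6 |
| 0.5 | 39.2 | 119 | ±7.2 |

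Unequal cough counts widen these further. A simulation with ICC 0.1 to 0.3 and a log-SD of counts of 0.8 to 1.2 (all assumed) gave half-widths of 4.6 to 10.2 points.

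**The case against.** The strongest reply is that the plan nowhere says that diagnostic accuracy is counted per cough. Section 9.1 offers the time pattern of a participant as an alternative signal, and it plans to add patient-specific information to the tool, which points towards prediction for a person. A registry in section 7.2 could be read as one participant's record. The per-sound definitions of true and false positives belong to secondary objectives 3 and 4. This stands: a reader might infer that the plan commits to per-cough accuracy, and it does not. But neither does it commit to the participant, and its wording for this objective is mostly about classifying coughs.

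Three other stronger readings also fail.
- **One heavy cougher could complete a diagnosis group.** That person could reach the cough count, but not the 200 series. They would supply 1 of 200 if a series is a participant, or about 30 of 200 if series are daily for a month.
- **Reaching 15,500 ends accrual.** The figure is an anticipation, and growth continues until performance plateaus. Section 9.2 also aims to put every participant with an etiologic diagnosis into the annotated datasets.
- **The plan's confidence intervals are too narrow.** It specifies none for this objective. The comparison above shows what would follow from treating coughs as independent.

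The illustrative accuracies, ICCs and cough rates are assumptions. Readings with a handful of patients and with 200 patients cannot both be true. They are shown because the text allows either.

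**Conclusion.** The point holds in conditional form. The documents establish four gaps: no number of patients or cap per diagnosis, an undefined time series, no stated unit for the primary accuracy measures, and no rule for reaching one diagnosis per participant.

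If the unit turns out to be the cough, the reported sensitivity is not the chance of diagnosing a patient. The gap depends on how cough counts and accuracy vary between patients; 86% against 59% is one assumed example. Treating coughs as independent would also overstate precision. On the reading of 200 patients and at 80% sensitivity, ±1.15 points compares with ±10.1 points for a per-patient result, and with ±2.5 to ±7.2 points for a per-cough result corrected for clustering (equal counts, ICC 0.05 to 0.5).

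Because this concerns the primary objective, it should be settled before accuracy is analysed. The participant target should be set while recruitment can still be steered, since analysis cannot supply missing patients later.

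**What to change.** **Sections 7.2 and 9.1.** Name the participant as the unit of the primary accuracy analysis. Prespecify how each participant's coughs, time pattern or both are combined into one score. The mean score over a fixed number of randomly drawn coughs is one option, though it drops the time pattern; the choice of method is the sponsor's. Report AUC, sensitivity and specificity over participants with participant-level 95% intervals. Keep per-cough figures as descriptive.

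**Section 9.2.** Define a time series and say how many one participant may contribute. Restate the target as participants per diagnosis (200, if that is what was meant). Limit or down-weight any one participant's share of the 15,500 coughs.

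**Cost.** This needs changes of wording and a modest amount of extra analysis. Intervals will be wider than per-cough ones, and the cough target will fill more slowly in chronic cough.

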#### Secondary objective 1:

We estimate needing 28 participants. This accounts for an anticipated effect size in the outcome (VAS score) of 0.35, with one predictor (cough frequency registered by Hyfe), and accounting for a loss of follow up of 10% of the participants. The significance level is set at 0.05, with a statistical power of 80%.

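### The 80% power cited for showing clinical evolution belongs to a regression of VAS on cough frequency; no power is shown for change, and no planned analysis tests whether the device tracks each patient's change

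*Combined protocol and SAP*

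**What the plan says.** Section 7.2 splits the primary efficacy question in two: predicting a diagnosis, and reflecting how patients evolve clinically. For the second part, section 9.2 (primary objective) says that for the capacity to "reflect changes in cough frequency associated to clinical evolution, sample size calculations are more straightforward and detailed below".

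Below that sentence, section 9.2 gives:
- **Secondary objective 1:** "We estimate needing 28 participants". The inputs are VAS as the outcome, an effect size of 0.35 whose index is not named, a model "with one predictor (cough frequency registered by Hyfe"), a 10% allowance for dropout, alpha 0.05 and 80% power.
- **Secondary objective 2:** no sample size.
- **Secondary objectives 3 and 4:** 24 participants, for the accuracy of cough detection.

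Section 9.1 (secondary objective 1) plans two kinds of analysis. The first is to "fit a linear regression model to compare self-reported VAS scores to daily cough frequency and calculate a correlation coefficient". The second is a paired t-test of average weekly VAS and of cough frequency, week 1 against study withdrawal, with a similar before-after comparison for the LCQ. The paragraph ends by saying that the approach should inform the system's capacity to "reflect clinical evolution of participants (Primary objective").

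**The concern.** The sample-size section points the clinical-evolution question at a calculation for something else. The 28 concerns whether VAS and cough frequency are associated. It contains no expected change, no SD of change and no within-patient correlation, and no other section supplies them. A reader would nevertheless take the 80% as the power of the evolution analysis.

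There is also a question of what the tests can show. A paired t-test of VAS asks whether average VAS moved, and one of cough frequency asks whether average cough frequency moved. Both can be significant when the device carries no information about which patients improved. The regression of daily VAS on daily cough frequency is a test of association, but it mixes differences between patients with changes within them. Patients who cough more may simply score higher throughout.

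At stake is half of the primary objective. It would carry a power figure that is not its own and rest on analyses that do not isolate the quantity of interest.

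**Working it through.** **1. Reproduce the 28.** Inputs from section 9.2, secondary objective 1: effect size 0.35 (index not named), one predictor, alpha 0.05, power 80%, loss 10%. Take 0.35 as Cohen's f². For one predictor, power = P(F′ > F₀.₉₅) with 1 and n − 2 degrees of freedom and noncentrality λ = f² × n.

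- n = 24: λ = 0.35 × 24 = 8.40; power 0.791.
- n = 25: λ = 0.35 × 25 = 8.75; critical F(1, 23) = 4.28; power 0.809.
- Loss: 25 / 0.90 = 27.8, rounded up to 28.

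The figure reproduces exactly. Other readings of 0.35 do not give it: as a correlation (two-sided, Fisher z), 62 evaluable and 69 after loss; as R², 17 and 19. Reading it as a standardised paired change does not give 28 either. The implied association is R² = 0.35 / 1.35 = 0.259, so r = 0.51. The calculation treats each participant as one independent observation.

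**2. What 25 evaluable participants give the paired tests.** The plan states no change or SD of change, so the standardised change d (mean change / SD of change) is an assumption, shown over a range. Two-sided alpha 0.05; noncentral t with 24 degrees of freedom, critical value 2.064, noncentrality d × √25 = 5d.

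| d (assumed) | Power, n = 25 |
|---|---|
| 0.2 | 16% |
| 0.3 | 30% |
| 0.5 | 67% |
| 0.58 | 80% |
| 0.6 | 82% |
| 0.8 | 97% |

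**3. Two significant paired tests without tracking.** Assume that VAS and cough frequency each improve by d = 0.8 and that the two changes are independent across patients. Each test has power 0.97, so both are significant with probability 0.97 × 0.97 = 0.94. The device's change then says nothing about any patient's VAS change, yet the planned before-after comparisons would look favourable 94% of the time.

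**4. Power of a change-to-change regression with 25 evaluable.** Same formula as step 1, with f² = r² / (1 − r²).

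- r = 0.51: f² = 0.35, λ = 8.75, power 0.81.
- r = 0.35 (illustrative; not a value from the plan): f² = 0.1225 / 0.8775 = 0.140, λ = 3.49, power 0.43.

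The Fisher z approximation for a correlation is somewhat lower. At r = 0.51, 0.562 × √22 − 1.96 = 0.67, giving about 75%. At r = 0.35, 0.365 × √22 − 1.96 = −0.25, giving about 40%. The conclusion is the same.

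**The case against.** Four points on the other side have weight.

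- **The arithmetic is right.** The 28 is correct for the association it sizes. The defect is a missing calculation and a cross-reference to the wrong one.
- **The closing sentence in section 9.1 may cover the regression too.** It ends a paragraph that opens with the regression, and it promises only information, not a powered test. If the regression is included, the 28 sizes part of what informs evolution. This stands as a reading. But the regression uses levels, and the calculation has neither a change term nor repeated measures, so within-patient change is still not sized.
- **28 is a stated need, not a cap.** Section 9.2 anticipates 200 cough time series for each diagnosis over up to five years, and section 4.1 asks participants for VAS and LCQ without limiting this to 28. If one diagnosis group gave about 199 evaluable participants (assuming one series each), a paired test would have 80% power at d = 0.2. This stands, and is why precision should be restated for the number enrolled.
- **The paired tests may be adequate even at 25.** Power is 82% at d = 0.6 and 97% at 0.8. This also stands.

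A reader might go further, carry the 0.35 over as a standardised before-after change, and conclude that the paired tests are badly underpowered. The documents do not support that. The 0.35 reproduces as f², which is a different index, and nothing in the plan transfers it.

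**Conclusion.** The concern holds in a limited form. Section 9.2 attributes the clinical-evolution question to a calculation that sizes the VAS-frequency association, and no power is shown for any analysis of change. With 25 evaluable participants the before-after tests reach 80% power at a standardised change of about 0.58 or more; whether that is expected cannot be judged from the plan. Independently of sample size, separate before-after tests do not show that the device tracks each patient's change, and the regression of daily levels does not isolate it.

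Two stronger conclusions are tempting but unsupported. Underpowering is not demonstrated, because no expected change is given and enrolment may exceed 28. Nor does the 28 automatically serve a change-to-change analysis: using f² = 0.35 there assumes that changes correlate at about 0.51, and the plan offers no basis for that.

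The figures rest on two-sided alpha 0.05, 10% loss from 28, one record per participant and approximately normal changes.

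**What to change.** **Section 9.1.** Name the analysis that answers the clinical-evolution question: a regression (or correlation) of each participant's change in VAS on their change in coughs per recorded hour, week 1 to the end of monitoring, one record per participant. Use change in LCQ as a supporting analysis. Keep the paired t-tests and before-after plots as descriptive.

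**Section 9.2.** Correct the statement that the evolution calculation follows below. Name the effect-size index as f². Say that the 28 sizes the VAS-frequency association. State that 25 evaluable participants give about 80% power for the change-to-change association only if r is about 0.51, and about 43% if r is 0.35 (illustrative). Restate the precision for the number actually enrolled.

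**Cost.** Rewording of two sections, using data already to be collected. The restatement itself requires no extra participants. The downside is that the stated power for the evolution question becomes conditional and less favourable.
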